4 DETERMINATION OF SAMPLE SIZE

Phase 1: Up to 6 subjects can be enrolled in up to 3 dose levels, there are 2 schedules being evaluated (Schedule A and Schedule B). Therefore, a maximum of 36 subjects are anticipated to be enrolled on this phase (not including subjects <12 months). Note: Subjects <12 months will not contribute to the determination of MTD/RP2D and data is for descriptive purposes only.

Phase 2: Up to approximately 75 subjects (approximately 25 in each histology group) will be enrolled. Simon's two-stage design will be used for each histology group. The following hypothesis will be tested at a one-sided 5% significance level:

$$H_0: p \leq 30\% \quad \text{Vs} \quad H_a: p \geq 55\%.$$

In the first stage, 9 subjects will be accrued. If there are 2 or fewer responses in these 9 subjects, the enrollment to this histology type (RMS, NRSTS, and EWS) will be stopped. Otherwise, 16 additional subjects will be enrolled in the second stage for a total of 25 subjects. The null hypothesis will be rejected if 12 or more responses are observed in 25 subjects. This design yields a type I error rate of 0.05 (one-sided) and the power of 80% when the true response rate is 55%.

5 STATISTICAL METHODS

Unless otherwise stated, tables, listings, and figures will be presented by dose level for Phase 1, and by histology type for Phase 2.

Descriptive statistics for continuous variables include: n, mean, standard deviation, median, 25th percentile (Q1), 75th percentile (Q3), minimum, and maximum. Categorical variables will be summarized as number and percentage of subjects.

5.1 Study Endpoints

5.1.1 Primary Endpoint(s)

The primary endpoints are:

- Phase 1: The MTD/RP2D of eribulin mesilate in combination with irinotecan hydrochloride in pediatric subjects with relapsed/refractory solid tumors, excluding CNS tumors. Note: Subjects <12 months will not contribute to the determination of MTD/RP2D and data is for descriptive purposes only.
- Phase 2: Objective response rate (ORR): defined as the proportion of subjects achieving a best overall response of confirmed partial or complete response, as determined by investigator assessment. Duration of response (DOR): defined as the time from the first date of documented PR or CR to the date of disease progression or date of death (whichever occurs first).

5.1.2 Secondary Endpoint(s)

Phase 1 & 2:

- Safety and tolerability: adverse events (AEs), serious adverse events, clinical laboratory values, ECG parameters, vital sign measurements and physical examinations.
- The pharmacokinetic profile of eribulin, irinotecan, and its active metabolite

Phase 2:

- Progression-free survival (PFS): defined as the time from the first dose date to the date of disease progression as determined by investigator assessment or death.
- The Clinical Benefit Rate (CBR): defined as the proportion of subjects with best overall response (BOR) of CR, PR, or durable SD based on RECIST 1.1 (durable SD is defined as SD with duration of >11 weeks).

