8.2 Secondary Objectives

Phase 1:

- To assess the safety and tolerability of eribulin mesilate in combination with irinotecan hydrochloride in pediatric subjects
- To determine the optimal schedule of irinotecan hydrochloride when administered with standard schedule (Day 1 and 8) of eribulin mesilate in pediatric subjects

Phase 2:

- To assess the Progression Free Survival (PFS) of eribulin mesilate in combination with irinotecan hydrochloride in pediatric subjects
- To assess the Clinical Benefit Rate (CBR) at 12 weeks of eribulin mesilate in combination with irinotecan hydrochloride in pediatric subjects

Phases 1 & 2:

- To evaluate the pharmacokinetic profile of eribulin, irinotecan and its active metabolite and compare to appropriate historical data

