9.5.1.3 Efficacy Assessments

9.5.1.3.1 TUMOR RESPONSE ASSESSMENTS

Tumor assessment will be performed based on RECIST 1.1. Investigator-determined response assessments at each assessment time point will be entered onto the appropriate CRF. Tumor assessments will be performed every 6 weeks until Week 12 and every 9 weeks thereafter on a fixed schedule. For Phase 1, neuroblastoma subjects can also be evaluated by meta-iodobenzylguanidine (MIBG) scintigraphy. For Phase 2, copies of scans for tumor assessments will be sent to an imaging core laboratory designated by the sponsor for quality assessment, archival, and potential independent review.

Computed tomography (CT) scans (with oral and intravenous contrast, unless clinically contraindicated) of chest, abdomen, and pelvis and other known sites of disease will be obtained at pre-study (within 28 days prior to Cycle 1 Day 1), and every 6 weeks thereafter (counting from C1D1), irrespective of dose delays. Magnetic resonance imaging (MRI) scans may be used instead of CT scans for abdomen and pelvis; however, chest must be assessed using CT. If only chest CT is performed then oral CT contrast is not required. The same method of assessment must be used at all time-points as used at pre-study. However, a chest x-ray may be used to identify new lesions in lieu of chest CT where appropriate (and after initial chest CT at screening). Post-screening scans may be performed without contrast if a medical contraindication develops while on study treatment. If iodinated IV contrast is contraindicated, chest CT should be done without IV contrast. MRI should be performed for all other body regions (with gadolinium unless contraindicated (eg, severe renal dysfunction)). An exception to the requirement for following chest disease by CT will be allowed where subjects have either non-parenchymal tumors, mediastinal and/or chest wall lesions. These

may be assessed (at Screening and post-baseline) using contrast-enhanced MRI. However, a chest CT is required at Screening for all subjects, and lung parenchymal lesions should be followed using CT (as per standard practice). If there is either an equivocal new lung lesion based on MRI or symptoms suggesting a new lesion, these should also be confirmed with chest x-ray or CT.

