Subjects with neuroblastoma (which can be included in phase 1 only) may have meta-iodobenzylguanidine (MIBG) scintigraphy and bilateral bone marrow biopsies assessments performed at sites where this is standard practice, at the discretion of the treating physician. This is an optional assessment for neuroblastoma subjects. Subjects that have positive lesions by MIBG scan at screening (within 28 days prior to administration of study drug) are not required to undergo PET or technetium-⁹⁹m bone scans. After identifying positive lesions at screening, repeat measurements may be performed within 4 weeks after confirmation of a PR or CR or as clinically indicated. Subjects with positive urinary catecholamines at baseline, should be assessed in cases of CR (catecholamines should be negative to confirm CR). Subjects with MIBG positive lesions at screening will be evaluable for MIBG response using the revised version of the International Neuroblastoma Response Criteria (INRC) scoring ([Brodeur GM, et al., 1993](#)).

All responses must be confirmed no less than 28 days following the initial assessment of response. In order for stable disease (SD) to be considered the best overall response, it must occur ≥ 5 weeks following the first dose of study drug.

All subjects will have an Off-Treatment Visit within 28 days after the last dose of study medication. Subjects that discontinue treatment without objective evidence of disease progression will continue to have tumor assessments performed as per the Schedule of Assessments until disease progression, death, or another anticancer therapy is initiated, whichever occurs first, unless the study is terminated. This follow-up data will be required unless consent is withdrawn.

After data cutoff for the primary analysis, tumor assessments may be performed as clinically indicated using the investigator's discretion, following the prevailing local standard of care.

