Urinalysis ^o	X				X			As clinically indicated					X							
					As clinically indicated for <12 months															
Tumor assessment ^p	X							Every 6 weeks (counting from date of first dose) until Wk 12, then every 9 weeks ^e					X							
Brain CT/MRI ^q	X	Clinically indicated and all timepoints for subjects with protocol-eligible treated brain mets at screening																		
Bone Scan ^r	X	Approximately every 24 weeks (in conjunction with scheduled tumor assessment) and as clinically indicated																		
Prior / concomitant medications ^s		Throughout																		
Adverse events/SAEs		Throughout																		
Subsequent anti-cancer treatments and survival														X						

a. Efforts should be made to conduct study visits on the scheduled day (+/- 3 days)

b. The Screening Period extends from Day -28 to Day -1. Computed tomography (CT) / magnetic resonance imaging (MRI) scans must be performed within 28 days prior to study drug administration. All clinical and laboratory studies to determine eligibility must be performed **within 7 days prior to study drug administration** unless otherwise indicated. Laboratory values used to assess eligibility must be no older than 7 days at the start of therapy.

- c. Assessments/procedures may be obtained within 72 hours prior to the start of the subsequent cycle.
- d. For logistical purposes, informed consent may be obtained from Day -29.
- e. Vital signs will be performed on Day 1 and Day 8 of each cycle for subjects aged ≥ 12 months and weekly for < 12 months.
- f. Height will be measured at Screening and on Day 1 of every other cycle starting from cycle 3.
- g. BSA based on a calculation at enrollment that is accepted and customarily used by the site, such as the Mosteller formula for children, adjustments to dosing to be made if 10% change in body weight.
- h. Performance status will be measured using Karnofsky or Lansky scales ([Appendix 2](#)).
- i. Women of childbearing potential require a negative urine or serum (depending on local practice) pregnancy test prior to starting treatment (within 7 days prior to study drug administration). Sexually active subjects must use an acceptable method of birth control. A separate baseline assessment is required if a negative screening pregnancy test was obtained more than 72 hours before the first dose of study drug. Thereafter, monthly pregnancy tests are required for sexually active subjects.

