Treatment phase: Tumor assessments of the chest/abdomen/pelvis and other areas of known disease that were scanned at screening, or newly suspected disease, must be performed every 6 weeks (within Week 6) during Treatment Cycles (or sooner if there is evidence of progressive disease) until Week 12 and then the frequency may decrease to every 9 weeks (or sooner if clinically indicated) thereafter for subjects that have CR, PR or SD and should utilize the same methodology (CT/MRI) and scan acquisition techniques (including use or nonuse of IV contrast) as were used for the screening assessments (see section 9.5.1.3.1 for exception on chest CT and more details). During the Follow-Up Period, subjects who discontinued study treatment without progression should have tumor assessments as per schedule of assessments until death, disease progression is documented or another anticancer therapy is initiated. After Week 12, these scans may be conducted every 9 weeks.
 - q. **Brain:**
Pre-study phase: Screening CT or MRI of the brain should be performed to assess potential for CNS disease and/or metastases between Day -28 and Day -1 for subjects with previously treated protocol-eligible brain metastases only.
Treatment phase: For subjects with previously treated protocol-eligible brain metastases, a brain scan must be performed at all tumor assessment time points. For all subjects, CT/MRI of the brain should be performed if clinically indicated. In subjects with body scans indicating a confirmed CR (according to RECIST 1.1), a CT/MRI of the brain will also be required within 1 week after the confirmation assessment to confirm the absence of brain metastases. The same methodology and scan acquisition techniques used at screening should be used throughout the study to ensure comparability.
 - r. A bone scan (whole body bone MRI, ^{18}F -NaF PET, or ^{18}FDG -PET to assess bone metastases will be performed at screening (within 6 weeks prior to first dose (historical scans acceptable) to establish a baseline, and then approximately every 24 weeks (in conjunction with scheduled tumor assessment) and as clinically indicated thereafter. The same methodology used at screening should be performed at all subsequent bone assessments.

- s. Information on anticancer treatment will be collected while subjects are in follow-up for disease progression.

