5.4.2 Secondary Efficacy Analyses

Progression-Free Survival

Progression-free survival (PFS) is defined as the time from the first study dose date to the date of disease progression (PD) as determined by investigator review or death (whichever occurs first). If a subject has not experienced PD or death, then the subject's data will be censored at the date of the last adequate radiologic assessment.

The PFS censoring rules in this SAP and definition of progression date follow the Food and Drug Administration (FDA) "Guidance for Industry Clinical Trial Endpoints for the Approval of Cancer Drugs and Biologics (2007)".

Table 2 Censoring Rules for Progression-free Survival Endpoint

Situation	End Date	Censored
Investigator documented PD	Date of the first assessment of the series of radiologic tests that determined PD	No
Death during the study before first PD	Date of death	No
No baseline or post baseline tumor assessments	Date of first dose	Yes
No progression and no death at the time of data cutoff	Date of last adequate tumor assessment* prior to data cutoff	Yes
Nonstudy anticancer treatment initiated before progression or death	Date of last adequate tumor assessment* prior to or on date of nonstudy anticancer treatment	Yes
Death or progression after more than one missed tumor assessments	Date of last adequate tumor assessment* prior to missed tumor assessments	Yes

PD = progressive disease.

* Adequate tumor assessment is radiologic assessment at regular interval as defined in the protocol.

Data cutoff generally refers to the data scope at each analysis (e.g., dry run or final analysis), from an executed cutoff or as of the final study data.

The distribution of PFS and time curve will be estimated using Kaplan–Meier method ([Kaplan and Meier, 1958](#)). Median survival time and the corresponding 90% CI will be estimated using Kaplan–Meier method for each histology type. PFS will also be graphically summarized by Kaplan–Meier curves for each histology type.

Clinical Benefit Rate

Clinical benefit rate (CBR) defined as the number of subjects with best overall response (BOR) of CR, PR, or durable SD based on RECIST 1.1, divided by the number of subjects in FAS, and corresponding confidence interval will be calculated. Durable SD is defined as SD with duration of more than 11 weeks.

The count and percentage of subjects with clinical benefit as well as exact 90% CI for the CBR will be summarized for each histology type.

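### The definition of durable SD does not exclude a child with SD at Week 6 and progression on the Week 12 scan, which can raise CBR

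*SAP*

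**What the plan says.** Both documents define CBR as the share of the Full Analysis Set whose best overall response is CR, PR or durable SD. SAP 5.1.2 states "durable SD is defined as SD with duration of >11 weeks", and SAP 5.4.2 repeats it: "Durable SD is defined as SD with duration of more than 11 weeks". The protocol synopsis, 9.7.1.1.2 and 9.7.1.6.2 use the same threshold. None of these places says when the duration starts, when it ends, or what the last qualifying scan must show. SAP 5.4.2 gives CBR an exact 90% confidence interval per histology, with no hypothesis and no target.

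The protocol objective (8.2) is "To assess the Clinical Benefit Rate (CBR) at 12 weeks of eribulin mesilate". The matching objective in SAP 3.1.2 has no time point.

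On scans, protocol 9.5.1.3.1 says "Tumor assessments will be performed every 6 weeks until Week 12 and every 9 weeks thereafter on a fixed schedule", with the clock running "every 6 weeks thereafter (counting from C1D1), irrespective of dose delays". Footnote p of the Phase 2 schedule (9.5.1.5, Table 14) says assessments "must be performed every 6 weeks (within Week 6) during Treatment Cycles", and footnote a gives study visits 3 days either side. For SD to be the best overall response, "it must occur ≥ 5 weeks following the first dose of study drug" (9.5.1.3.1).

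Table 2 in SAP 5.4.2 dates progression to the scan that shows it, but the table is for PFS only. SAP section 9 leaves derivation rules to separate documents.

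**The concern.** Under this schedule the Week 12 scan is the first planned assessment that can show whether a child with SD at Week 6 still has disease control at 12 weeks. Growth between the two scans is normally discovered, and dated, at Week 12. A duration that ends on the progression date therefore credits the child with the whole interval up to the scan that showed failure. One Week 6 scan is enough for a best response of SD, so nothing else in the text removes this child from the numerator.

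The stake is the meaning of a secondary endpoint. On that reading, CBR is close to the proportion not yet progressed at Week 6, while the protocol objective describes benefit at 12 weeks. The trial is single-arm, open-label and investigator-assessed, so the classification rule should be settled before the results are known.

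**Working it through.** The documents state no expected CBR, sample size or power for CBR, so there is no figure of the plan's to reproduce.

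**Inputs.** First dose at C1D1; Week 6 = 42 days and Week 12 = 84 days (protocol 9.5.1.3.1); visit window of 3 days either side (9.5.1.5); threshold 11 × 7 = 77 days (SAP 5.1.2); about 25 subjects per histology (SAP 4).

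**1. The child with SD at Week 6 and progression at Week 12, under three readings of duration**

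| Reading | Duration | More than 11 weeks? |
|---|---|---|
| (a) First dose to progression scan | 84/7 = 12.0 weeks; with ±3 days, 81/7 = 11.57 to 87/7 = 12.43 | Yes, counted |
| (b) First dose to last SD scan | 42/7 = 6 weeks | No |
| (c) First SD scan to progression scan | (84 − 42)/7 = 6 weeks | No |

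**2. Which reading the documents lean towards.** The only timing rule for SD (at least 5 weeks, protocol 9.5.1.3.1) counts from first dose. PFS starts at first dose, and both durations that the SAP defines, PFS and DOR, end at progression or death (5.1.1, 5.1.2, 5.4.2). Together these point to (a), but no passage applies them to SD.

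**3. Is the 11-week threshold itself at fault?** A Week 12 scan done 3 days early falls at 81 days = 11.57 weeks. A child still in SD on that scan should count, and a literal 12-week cut-off would drop that child. The threshold is a sensible allowance for an early scan. What is missing is the scan requirement.

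**4. Effect per child, if (a) is used.** Each such child adds 1/25 = 4 percentage points. Illustration with exact (Clopper-Pearson) 90% intervals:

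- 8/25 = 32% (17.0% to 50.4%)
- two more children: 10/25 = 40% (23.6% to 58.3%)
- five more children: 13/25 = 52% (34.1% to 69.5%)

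**5. How many children could be affected.** The documents give no PFS assumption, so I assume exponential PFS with median m weeks. The probability of an event between Weeks 6 and 12 is exp(−6L) − exp(−12L), with L = ln 2 / m.

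| Median m | Event-free at Week 6 | Event-free at Week 12 | Difference | Per 25 |
|---|---|---|---|---|
| 8 weeks | 0.595 | 0.354 | 0.241 | 6.0 |
| 12 weeks | 0.707 | 0.500 | 0.207 | 5.2 |
| 16 weeks | 0.771 | 0.595 | 0.177 | 4.4 |

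These are upper bounds. They include deaths, progressions found on unscheduled scans before 11 weeks (which fail the threshold even under (a)), and responders, who qualify through CR or PR anyway.

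**The case against.** The strongest reply is that the text does not say the duration ends at progression. The PFS rules are headed for PFS. Readings (b) and (c) give 6 weeks and exclude the child, and the unseen programming specifications may adopt one of them. This stands as far as it goes: a reader might infer that the definition necessarily counts these children and therefore inflates CBR, and the documents do not establish that. But leaving the choice to a programming document is not a good answer when the SAP itself fixes start and end dates for PFS, and when its own conventions lean towards the reading that counts the child.

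A reader might also infer that an 11-week threshold contradicts an objective at 12 weeks. It does not; it matches the early edge of the Week 12 scan, much as the 5-week rule does for the Week 6 scan.

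Nor does the ±3-day window reverse the classification. From 81 to 87 days every scan exceeds 77 days, and it would take a scan about 7 days early to change the result.

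Finally, CBR has no test or stopping rule attached, and the Kaplan-Meier PFS curves show progression around Week 12 separately. That is correct, and it limits the consequence to how CBR is reported and interpreted.

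**Conclusion.** The point holds as an incomplete definition. Durable SD has no start, no end and no required progression-free scan, and under the reading closest to the SAP's other time-to-event definitions a child who has progressed at Week 12 is reported as having clinical benefit. If that reading is used, CBR rises by 4 percentage points per such child at n=25. The proportion affected is at most 24% to 18% for median PFS of 8 to 16 weeks, and this rests on an assumed exponential distribution and assumed medians. If the duration ends at the last SD scan, or starts at the first one, the effect is nil. The primary endpoint, the futility rule and the go/no-go decisions are untouched. The clarification is worth making because the most natural way to fill the gap misclassifies children at the scan that decides the endpoint.

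**What to change.** In SAP 5.1.2 and 5.4.2, and in the matching protocol text (synopsis, 9.7.1.1.2 and 9.7.1.6.2), keep the 11-week threshold and add wording to this effect:

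> Durable SD requires a tumor assessment 11 weeks (77 days) or more after first dose, that is the Week 12 scan or a later one, showing SD or better with no earlier progression. Progression on that scan is not clinical benefit, unless the subject already qualifies through CR or PR.

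This keeps the child still in SD on a Week 12 scan at 81 days and excludes the child who has progressed on it. It also covers a missed Week 12 scan, because a later scan must then show no progression. All five places should change together so that the documents stay consistent.

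The cost is a sentence or two in each place, settled before the Phase 2 results are reviewed. The reported CBR may be lower, and a child with SD at Week 6 and no later scan would not count.

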5.2 Study Subjects

5.2.1 Definitions of Analysis Sets

The following analysis sets will be defined:

- **Full Analysis Set (FAS)** will consist of subjects who receive at least 1 dose of either study drug.
- **Safety Analysis Set** will consist of subjects who receive at least 1 dose of either study drug.
- **Pharmacokinetic Analysis Set (PAS)** will include subjects who have documented dosing history and at least one post-dosing quantifiable drug concentration.
- **Dose Evaluable Set (DES)** for Phase 1 will consist of all subjects who completed Cycle 1 treatment and were evaluated for DLT, and those who discontinued during Cycle 1 due to DLT. DES will be used for evaluation of each dose level for dose-escalation and for determination of MTD.

